### ***Influenza and other respiratory virus testing***

Data on all influenza and other respiratory virus test results will be extracted for all members of the cohort during the surveillance period. For each test result, sites will provide data on encounter type associated with the lab test, diagnoses (based on ICD code) associated with encounter during which testing occurred, date of specimen collection, type of test performed and test result. Network sites will provide information on how laboratory testing data was pulled (for example, through use of CPT or other procedure codes or from laboratory databases). For a subset of patients (number to be determined by joint consensus by the collaborating partners), accuracy of extracted laboratory data will be verified through manual review of source data (i.e. medical chart review or review of laboratory databases). Respiratory viruses for which data will be collected, in addition to influenza, include respiratory syncytial virus, adenovirus, parainfluenza virus, human metapneumovirus, rhinovirus, enterovirus, coronaviruses, and other viruses, including novel viruses.

### ***High risk conditions***

For the primary objectives, high risk conditions will be defined using ICD diagnosis codes. A patient with at least 1 inpatient encounter or at least 1 outpatient encounter with a high-risk ICD diagnosis code (see Appendix D) recorded in the 12 months prior to the current influenza season will be considered as having a high-risk condition. The following high-risk conditions will be defined:

- Chronic lung disease;
  - Asthma;
  - COPD;
  - Pulmonary tuberculosis
  - Endemic mycoses

- Chronic metabolic disease;
  - Diabetes mellitus;
- Blood disorders;
- Cardiovascular disease;
  - Coronary artery disease;
  - Heart failure;
  - Congenital heart disease;
- Neuromuscular disorder;
- Neurologic disorder;
- Immunocompromised condition;
  - Solid organ malignancy;
  - Hematologic malignancy;
  - Solid organ transplant;
  - Hematopoietic stem cell transplant;
- Chronic renal disease;
- Gastrointestinal/liver disease;
- Rheumatologic/Autoimmune condition.

Additional underlying conditions, including, but not limited to, pregnancy, sickle cell disease, hypertension, obesity, and cystic fibrosis have also been associated with increased risk of severe influenza or COVID-19 disease and thus might be further defined and explored in the network.

### ***Data on healthcare utilization***

Healthcare utilization is an important data element to consider for the primary objectives. The use of healthcare directly informs the definition of each of the seasonal cohorts and also is

known to be associated with subsequent care for influenza and other respiratory virus infections as well as the propensity for seasonal influenza vaccination. Healthcare utilization will be captured using data on the number of telemedicine encounters, office-based encounters, and inpatient hospital admissions, for any reason, that occurred prior to the start of influenza season, during the influenza, and, for those who remain in the cohort, after the end of influenza season.

To better understand healthcare utilization patterns in the cohort, among vaccinated individuals, and among those with respiratory-associated inpatient or outpatient visits, several different categories of healthcare encounters will be enumerated in the 12 months before, during, and 12 months after each influenza season.

- Primary care encounters include office-based visits that occurred in a general pediatric, general internal medicine, med-peds, general family medicine, or obstetrics/gynecology practice.
- Telemedicine/telehealth encounters include any call for a clinical consultation
- Medical specialty care encounters include office-based visits that occurred in a practice for cardiology clinic, diabetes clinic, rehabilitation clinic, gastrointestinal specialist, etc. Excluded visits are those that are for laboratory only, imaging only, or nurse only.
- Urgent care encounters.
- Emergency department encounters include visits to the emergency department that did not result in an inpatient admission.
- Inpatient hospital admissions include admissions to an inpatient ward or an observation unit.

| Vaccine Type | Age group                     |
|---------------------|--------------------------------------|
| SARS-COV-2          | All ages (as licensed and available) |

***Data on other exposures of interest***

Individual level data will be extracted and provided on:

- Patient age as of the start date of the observation period,
- Sex
- Race and ethnicity
- Date of enrollment in the membership health plan or date of first qualifying healthcare encounter in the 12 months prior to influenza season (the encounter that included the individual into the cohort)
- Primary, secondary, tertiary and quaternary insurance type

**5.5 Outcomes of Interest**

- Respiratory illness-associated hospitalizations with laboratory-confirmed influenza
  - Respiratory hospitalizations will be defined using ICD-9 and ICD-10 discharge diagnoses codes as listed in Appendix D.
  - Data on all respiratory hospitalizations will be collected for the entirety of the surveillance period (influenza season).
  - The respiratory hospitalizations will be linked with data on influenza testing to determine if the hospitalization was associated with laboratory-confirmed influenza.
    - Laboratory-confirmed influenza associated respiratory hospitalization will be defined by a positive influenza test within 14 days prior to hospitalization or no more than 3 days after hospital admission.

- Hospitalization will be defined as admission to an inpatient ward or an observation unit. Time spent only in the emergency department will not count as a hospitalization.
- Re-admissions that occur within 30 days of the index hospitalization will be counted as part of the index hospitalization. Readmissions that occur >30 days after the index hospitalization will be considered new hospitalization events.
- ICU admission among persons hospitalized with laboratory-confirmed influenza-associated respiratory hospitalization
- Invasive mechanical ventilation among persons hospitalized with laboratory-confirmed influenza-associated respiratory hospitalization
- In-hospital death among persons hospitalized with laboratory-confirmed influenza-associated respiratory hospitalization
- Acute respiratory illness-associated outpatient visits with laboratory-confirmed influenza
  - Acute respiratory illness-associated outpatient visit will be defined using the ICD-9 and ICD-10 discharge codes listed in Appendix D.
  - Data on all acute respiratory illness-associated outpatient visits will be collected for the entirety of the surveillance period (influenza season).
  - The acute respiratory illness outpatient visit will be linked with data on influenza testing to determine if the visit was associated with a positive influenza laboratory test.

Appendix D provides a more detailed list of the variables used to define outcomes of interest.

[figure not shown]
## **5.6 Summary of Data Elements for Primary Objectives**

Please see Appendix B for more detailed list of data elements

[figure not shown]
- For the entire cohort:

- Demographic information (age, sex, race, ethnicity)
- Date of enrollment in health plan and/or date of first encounter in the health system in the 12 months before the start of influenza season (as applicable)
- Healthcare utilization (primary/secondary insurance type, number of medical encounters before and during influenza season). This is further defined to be the monthly number of healthcare encounters by setting (general practice, medical specialty, emergency department, urgent care, telehealth, or inpatient).
- Underlying high risk medical conditions (derived from ICD codes)
- Vaccination status (influenza and other vaccinations received dating back to 2010)
- All hospitalizations and outpatient encounters with respiratory virus testing during influenza season of interest:
  - Date of encounter (or date of admission)
  - Date of testing
  - Clinical setting
  - Influenza and other respiratory virus test type and result
  - Diagnosis codes from the encounter/admission
- Respiratory syndrome-associated hospitalizations during influenza season of interest:
  - Hospital admission and discharge dates
  - Diagnosis codes
  - Severe outcomes (ICU admission, mechanical ventilation, in-hospital mortality)
- ARI syndrome-associated outpatient encounters during influenza season of interest
  - Encounter date
  - Diagnosis codes

Data streams for entire cohort during to-be-determined lead-in period:

[figure not shown]

Data streams for influenza season of interest:

[figure not shown]

All sources should be linked by subject ID  
 \*For influenza and other vaccinations received dating back to 2010, where possible.

Data streams for entire cohort during to-be-determined lead-in period:

Data streams for influenza season of interest:

All sources should be linked by subject ID  
 \*For influenza and other vaccinations received dating back to 2010, where possible.

## **5.7 Summary of Methods for Secondary Objectives**

After the primary objectives are met, a set of secondary objectives will be addressed with a deeper level of data collection or analysis. Funding of data collection or analysis for these secondary objectives will depend on resources and success of the primary objectives. Secondary objectives may involve some but not necessarily all participating sites.

The secondary objectives include capturing and assessing the validity of additional data elements (such as laboratory values, vital signs, and medications) to better characterize underlying medical conditions and severity of influenza virus infections. It is anticipated that the methods for assessing the validity of the additional data will be similar to the methods used to validate data for the primary objectives, including comparison of extracted data to data in the primary data source, searching for deviations from expected values, and comparing findings to external sources.

In addition to expanding the data elements being captured, sites participating in the secondary objectives may be asked to extract data from the 2019–2020 influenza season, to submit “prospective”, or near real-time, data from the 2020–2021 influenza season, or to expand outcome ascertainment beyond the pre-defined influenza season.

As more details of the methods for the secondary objectives are discussed and consensus reached with the participating sites, the methods and protocol will be amended.

## **6.0 Statistical Analysis**

### **6.1 Analysis Plan**

***Objective 1: Assess the validity and biases associated with defining the source population based on care-seeking***

Correctly capturing the health system's denominator is a critical component of the study objectives, thus all health systems will be asked to validate the eligibility definitions using their information from their membership or source population.

- Compare the demographics of participants defined using the five inclusion criteria, using appropriate bivariate statistics as appropriate.
- Compare, using appropriate bivariate statistics, the healthcare utilization between all known members and those participants defined using the five inclusion criteria.
- Compare the frequency of respiratory-associated hospitalization between the cohorts as defined using the five inclusion criteria.

***Objective 2: Validation of influenza vaccination data***

- Describe the frequency of influenza vaccination among cohort members and vaccine type received. Descriptions will include the full cohort and will be stratified by individual characteristics such as age group, high-risk condition, and prior healthcare utilization.
  - Frequency of vaccination will be compared across strata using appropriate bivariate statistics (e.g. chi-square tests or Fisher's exact tests).
- Among those determined to be vaccinated for influenza
  - Assess the proportion that were identified through various data sources (e.g., procedure codes from a medical visit, other notation in the medical chart, vaccine registry, billing data, etc.). Assess whether the source of vaccination data varies by individual characteristics, including age group, high-risk conditions, and prior healthcare utilization.

- Compare the completeness and consistency of data on date of vaccination and vaccine type between data sources and by patient characteristics such as age group, high-risk conditions, and prior healthcare utilization.
- Comparisons of data by source, for completeness, and for consistency and how these differ by patient characteristics will be conducted using appropriate bivariate tests of association and/or multivariate regression. As an example, regression analyses could include data source as the outcome of interest with patient characteristics as explanatory variables.
- Describe the timing of vaccine receipt among cohort members by age group, high risk condition, prior healthcare utilization, and vaccine type received.

This description will be explored using a variety of methods, including time to vaccination, median week of vaccination, or frequency of vaccination at least two weeks prior to the start of influenza circulation. Comparison of timing by patient characteristics will be conducted using methods appropriate to the outcome type; for example, proportional hazards modeling for time to vaccination.

***Objective 3: Biases associated with clinical testing***

- Describe the frequency of clinical testing for influenza and other respiratory viruses in the cohort during an influenza season by setting (inpatient vs. outpatient), age group, high-risk status, influenza vaccination, prior healthcare utilization, and timing of encounter within the season.
- Describe the diagnoses associated with visits where clinical testing for influenza and/or other viruses was performed.

- Among hospitalizations with respiratory illness during the influenza season, describe the frequency and types of clinical testing used.
  - Characteristics and predictors of receipt of diagnostic test for influenza will be assessed using bivariate tests of association and/or multivariate regression with receipt of test as outcome of interest and patient and clinical characteristics (including age, vaccination status, high-risk conditions, timing of the clinical encounter within the season, prior healthcare utilization, diagnoses, etc.)
- Among outpatient visits for ARI during the influenza season, we will describe the frequency and types of clinical testing used.
  - Characteristics and predictors of receipt of diagnostic test for influenza will be assessed using bivariate tests of association and/or multivariate regression with receipt of test as outcome of interest and patient and clinical characteristics (including age, vaccination status, high-risk conditions, timing of the clinical encounter within the season, prior healthcare utilization, diagnoses, etc.)

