### 4.1 Primary Objectives

1. Assess the validity and biases associated with defining the source population based on care-seeking.
  - Compare characteristics of the different cohorts, as defined above, assessing differences in the demographics, the frequency of underlying high-risk conditions, and the frequency of respiratory hospitalizations during influenza season.
2. Assess internal and external validity of influenza vaccination data for current and prior seasons.
  - Internal validity:
    - Assess the accuracy of the derived vaccine status variable in relation to a manual review of records on a subset of the cohort.
    - Describe the contributions to the overall conclusion about vaccination status by various sources from which vaccination data were obtained.
    - Describe the consistency of vaccination data that are available by data source, including date of vaccination, vaccine type, vaccine route, vaccine

lot number, setting in which vaccine was administered, number of doses of vaccine (children <9 years).

- Describe completeness of vaccination data (e.g. date of vaccination, type of vaccine, lot number) by data source for the current season and prior seasons.

- External validity:

- Compare vaccine coverage and data completeness to values reported from other studies with active enrollment / prospective data collection.

3. Assess biases associated with clinical testing for influenza and other respiratory viruses and whether they differ in the inpatient versus outpatient setting:

- Assess the accuracy of the extracted test dates, types, and results in relation to a manual review of records on a subset of the cohort.
- Estimate proportion of cohort enrollees tested for influenza and other respiratory viruses during the influenza season.
- Describe types of influenza and other respiratory virus tests performed on cohort enrollees by pediatric and adult age groups and how test types vary by setting.
- Estimate the proportion of respiratory hospitalizations tested for influenza during the influenza season and factors associated with influenza testing in the inpatient setting including age, high-risk conditions, current season influenza vaccination status, ICU stay, timing of encounter within season, diagnoses codes.

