- Estimate the proportion of outpatient visits for acute respiratory illness (ARI) that were tested for influenza and factors associated with influenza testing in the outpatient setting including age, high-risk conditions, current season influenza

vaccination status, visit type, timing of encounter within influenza season, diagnoses codes.

4. Measure the incidence of health outcomes related to influenza by pediatric and adult age groups as outlined below. The incidence of these outcomes will be assessed by age groups, demographic characteristics, influenza type/subtype, and high-risk conditions:
  - Laboratory confirmed influenza-associated respiratory hospitalizations.
  - ICU admission among persons with laboratory-confirmed influenza-associated respiratory hospitalizations.
  - Invasive mechanical ventilation use among persons with laboratory-confirmed influenza-associated respiratory hospitalizations.
  - In-hospital death among persons with laboratory-confirmed influenza-associated respiratory hospitalizations.
  - Laboratory-confirmed influenza among persons with outpatient visits for acute respiratory illness.
  
5. Estimate the effectiveness of current season influenza vaccine in preventing the below outcomes by age groups, influenza type/subtype, and high-risk conditions:
  - Laboratory confirmed influenza-associated respiratory hospitalizations (all ages).
  - ICU admission among persons with laboratory-confirmed influenza associated respiratory hospitalizations (all ages).
  - Laboratory-confirmed influenza among persons with outpatient visits for acute respiratory illness (pediatrics; adults if outpatient influenza testing permits).

Appendix A presents the main outcomes, exposures, and modifiers of interest for the primary and secondary study objectives. Appendix B provides the data dictionary of analytic variables needed to meet these objectives.

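### Objective 3 asks whether testing biases differ between inpatients and outpatients, but section 6.1 states no contrast of the predictor associations between the two settings

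*Protocol*

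**What the plan says.** Protocol section 4.1, Objective 3, sets the aim of assessing biases in clinical testing and "whether they differ in the inpatient versus outpatient setting". Its sub-aims are then setting-specific. For inpatients they cover "factors associated with influenza testing in the inpatient setting including age, high-risk conditions, current season influenza vaccination status" and further items including ICU stay. For outpatients the sub-aim is "Estimate the proportion of outpatient visits for acute respiratory illness (ARI) that were tested for influenza and factors associated with influenza testing", with a similar list that has visit type where the inpatient list has ICU stay.

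Protocol section 6.1, Objective 3, has three relevant parts:

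- Testing frequency in the cohort is described "by setting (inpatient vs. outpatient), age group, high-risk status, influenza vaccination, prior healthcare utilization, and timing of encounter within the season".
- For inpatients: "Among hospitalizations with respiratory illness during the influenza season, describe the frequency and types of clinical testing used", followed by the predictor analysis, "Characteristics and predictors of receipt of diagnostic test for influenza will be assessed using bivariate tests of association and/or multivariate regression", with receipt of a test as the outcome.
- For outpatients: "Among outpatient visits for ARI during the influenza season, we will describe the frequency and types of clinical testing used", followed by the same predictor sentence and the same open-ended covariate list.

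Appendix A lists healthcare setting for Objective 3 among the stratification variables. Appendix D defines respiratory encounters by a shared code list. It adds sign and symptom codes for outpatient clinic, telehealth, emergency department and urgent care encounters only.

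**The concern.** A question about whether an association differs between two groups is answered by estimating the difference, with its uncertainty. Section 6.1 yields two separate sets of associations and stops there. Because the method is bivariate tests and/or regression, bivariate tests alone would satisfy the text, and adjusted effects that could be set against each other are not guaranteed.

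Describing testing frequency by setting shows whether the level of testing differs. It does not clearly show whether testing depends on vaccination, age or high-risk status to a different degree in the two settings, which is the bias question.

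The question matters because Objectives 4 and 5 count laboratory-confirmed outcomes found through clinician-driven testing in both settings. A reader comparing inpatient with outpatient incidence or vaccine effectiveness (VE) needs to know whether selection into testing differs between them, and how precisely that is known.

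**Working it through.** **1. Is a contrast stated anywhere for Objective 3?** Section 6.1 was compared across objectives.

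| Objective | Comparison named in section 6.1 |
|---|---|
| 1 | Cohorts under the five inclusion criteria are compared |
| 2 | Vaccination frequency is compared across strata; completeness and consistency are compared between data sources |
| 3 | Frequency described by setting; predictors assessed within each setting; no contrast of associations |
| 4 | Risk groups compared by rate differences or relative rates |
| 5 | VE estimated by site, then heterogeneity across sites examined |

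The other four objectives name a comparison or heterogeneity step. Objective 3 poses a between-group question and names none for the associations.

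**2. Is there a plan figure to reproduce?** No. Objective 3 gives no number of encounters, testing proportion, effect size, alpha or power, and Table 1 in section 6.2 concerns VE only. Every input below is an assumption.

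**3. If significance were compared across settings, how often would it mislead?** Assume half of encounters are in vaccinated people, the same true odds ratio (OR) in both settings, two-sided alpha 0.05 and independent settings. The tested proportion among the unvaccinated is either (a) 40% in both settings or (b) 50% inpatient and 10% outpatient.

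- SE(log OR) = sqrt(sum of 1/expected cell count).
- Power in a setting is the Wald test power for log OR / SE.
- P(exactly one significant) = P_in(1 − P_out) + P_out(1 − P_in).

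Worked case: OR 1.2, 1,000 against 10,000 encounters, (a). P_in = 0.296 and P_out = 0.994, so 0.296 × 0.006 + 0.994 × 0.704 = 0.70.

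| True OR in both | Inpatient / outpatient encounters | P(exactly one significant), range over (a) and (b) |
|---|---|---|
| 1.2 | 1,000 / 10,000 | 0.62-0.70 |
| 1.1 | 5,000 / 50,000 | 0.59-0.62 |
| 1.2 | 5,000 / 50,000 | 0.10-0.11 |
| 1.3 | 5,000 / 50,000 | 0.004 |

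A direct test of the log ratio of ORs has a nominal 5% false-positive rate in every row.

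**4. The opposite error.** Take true ORs of 1.2 inpatient and 1.5 outpatient, with 5,000 and 50,000 encounters. Both separate tests are significant with probability 0.89-0.90, so a significance comparison would usually show no difference. The direct contrast, with SE = sqrt(SE_in² + SE_out²), has power 0.94-0.96.

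**5. A single numerical picture.** Assume 5,000 hospitalizations with 50% tested, 200,000 outpatient visits with 20% tested, and half of each vaccinated.

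- Inpatient SE = sqrt(4/1,250) = 0.0566.
- Outpatient SE = sqrt(2/20,000 + 2/80,000) = 0.0112.
- SE of the log ratio = sqrt(0.0566² + 0.0112²) = 0.0577.
- An OR of 1.10 in both gives 0.98-1.23 (p = 0.09) inpatient and 1.08-1.12 (p < 0.001) outpatient, with ratio 1.00 (0.89-1.12).
- ORs of 1.25 (1.12-1.40) and 1.05 (1.03-1.07) are both significant, with ratio 1.19 (1.06-1.33).

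**6. Comparability of the two denominators.** The covariate lists in section 6.1 are the same for both settings, and vaccination status, age, high-risk conditions and timing in season are common to both. The encounter definitions are not the same, because the symptom codes in Appendix D enter only outside the hospital. A ratio of effects would therefore mix any difference in testing behaviour with a difference in case definition.

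**The case against.** The strongest reply is that the protocol never says the settings will be judged by which predictors reach significance. Regression gives estimates and intervals, and the ratio of two ORs can be derived from two separate fits, as step 5 does. This stands. A reader might infer that sample size will decide what looks like a difference, or that comparing significance is the only answer available. The documents support neither.

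A second reply is that the settings are in fact compared: testing frequency is described by setting, and section 4.1 asks how test types vary by setting. This stands for frequencies and test types. The frequency description might even be cross-classified by vaccination status and setting, although the text does not say so. It does not supply a contrast of adjusted associations.

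A reader might also infer from the ICU-stay and visit-type items in section 4.1 that the two analyses use incompatible models. Section 6.1 gives identical, open-ended covariate lists, so that does not follow.

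Third, the form of a contrast is often left to a statistical analysis plan, which is not at hand and could add one. That is fair for technical detail such as clustering. But section 6.1 is the protocol's own analysis plan and names the comparison for the other objectives, so the omission for a stated primary question is a mismatch within the document.

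Finally, hospitalization VE and outpatient VE are separate analyses, and a cross-setting ratio corrects neither. That is true. The contrast serves the question posed in Objective 3 and the reading of the two sets of results together. It is not a bias correction.

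**Conclusion.** The point holds as a mismatch between question and analysis. Objective 3 asks whether testing biases differ by setting, and section 6.1 fixes a frequency description and two parallel predictor analyses, with no contrast of the associations and no stated uncertainty for the difference.

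The practical harm is conditional. If significance were compared, the chance of a spurious difference runs from about 0.6-0.7 to 0.004 across the assumed cases. That range depends on effect sizes and encounter numbers that the protocol does not give, so no single magnitude can be claimed. The documents do not support the stronger conclusion that the study will misreport a difference, or that readers will take one setting to be free of testing bias. The change is worth making because it is cheap and the question belongs to a primary objective.

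**What to change.** Add to section 6.1, Objective 3:

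- Fit one model over both settings with a common covariate set and setting-by-predictor interactions for the shared predictors: vaccination status, age group, high-risk status and timing in season. Cluster standard errors on person, since one person can contribute encounters in both settings.
- Report the inpatient/outpatient ratio of each adjusted effect with its 95% CI.
- Run this, at least as a sensitivity analysis, on encounters that meet the Appendix D codes shared by both settings, leaving out the symptom codes that apply only to outpatient-type encounters.
- Keep the setting-specific models as descriptive.
- State that the ratio partly reflects case mix and baseline testing differences and is not a pure difference in bias.

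If the contrast is not wanted, reword Objective 3 in section 4.1 to separate description by setting.

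The cost is one additional model, plus the sensitivity run, on data already to be extracted. No new data collection is needed. The drawback is that the ratio needs the stated caveat to be read correctly.
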